Risk of discomfort during EEG: The EEG headset allows adjustments to reduce scalp pressure if it is uncomfortable. EEG recording will be aborted if it cannot be done comfortably for any subject.

Risk during MRI procedures: Subjects will fill out standard questionnaires and informed consent provided by the Brown MRI research facility (MRF). Subjects will be screened for metallic objects or exposure that would preclude them from participation in the study. Investigators and research technicians associated with the MRF will screen for claustrophobia. If there is concern for a physical abnormality on structural scan, the principal investigator will provide an appropriate clinical referral. Ear protection will be provided to reduce the noise level. Participant may stop during the procedure for any reason by telling the technician through the intercom or by squeezing a ball that we will place in the participant's left hand.

Subjects will be told the following, which is reiterated in the ICF: "during the scan itself, you will lie on a table that slides into a horizontal cylinder slightly wider than your body. You will be asked to lie still, but you will be able to hear and speak to the MRI personnel. If you feel uncomfortable for any reason before or during the procedure, please tell the researcher. If for any reason during the procedure you want to stop, you may do so at any time by telling the technician through the intercom or by squeezing a ball that we will place in your left hand. This ball is connected to a buzzer that tells us you want to stop."

D2. Measures to ensure confidentiality:

Subjects will be told that their participation in this study is strictly voluntary and that they can change their minds at any time without impacting their present or future research participation. They will be assured of confidentiality in the handling of data generated by their participation in this study.

Subjects will also be informed that their participation in this study and the clinical information relevant to safe treatment with sTMS will be documented in the Butler Hospital medical record. Other research-related information will be stored in locked research files in the Mood Disorders Research Clinic and subject names will not appear on any research forms (only identification

numbers). Data will be stored on secure hospital servers and in secure, password-protected REDCAP databases.

Confidentiality: Information about study subjects will be kept confidential and managed according to the requirements of the Health Insurance Portability and Accountability Act of 1996 (HIPAA). Those regulations require a signed subject authorization informing the subject of the following: What protected health information (PHI) will be collected from subjects in this study; Who will have access to that information and why; Who will use or disclose that information; The rights of a research subject to revoke their authorization for use of their PHI.

In the event that a subject revokes authorization to collect or use PHI, the Investigator, by regulation, retains the ability to use all information collected prior to the revocation of subject authorization. For subjects that have revoked authorization to collect or use PHI, attempts will be made to obtain permission to collect at least vital status (i.e. that the subject is alive) at the end of their scheduled study period.

Ethical Considerations: This study is to be conducted according to US and international standards of Good Clinical Practice, applicable government regulations and Institutional research policies and procedures. This protocol and any amendments will be submitted to a properly constituted independent Institutional Review Board (IRB), in agreement with local legal prescriptions, for formal approval of the study conduct. All subjects for this study will be provided a consent form describing this study and providing sufficient information for subjects to make an informed decision about their participation in this study.

D.3. data safety monitoring plan:

Study Monitoring Plan: This study will be monitored with regard to progress, adverse events, and other unexpected events at weekly research staff meetings with the investigators. The Butler IRB will provide review and oversight of progress through continuing review and through review of Serious/Unexpected Adverse Events. A data safety monitoring board will be convened annually to review the progress. Together these measures will act to ensure its scientific integrity, the quality of data, the safety of human subjects, and compliance with the ethical principles that have their origin in the Declaration of Helsinki, the ICH guideline for Good Clinical Practice (GCP), applicable local regulatory requirements, and Sponsor regulations, guidelines, and policies.

E. Potential Benefits

For Subjects: Benefits to subject's participation in this trial include a thorough evaluation of depressive symptoms at no cost, and possible relief from BDD symptoms from an investigational treatment with a favorable side effect profile.

For Society: The potential benefits of this project to society may include enhanced knowledge about treatment options for BDD.

F. Risk-Benefit Ratio

The risk-benefit ratio of this study is favorable. Risks of adverse events associated with the use of this device (rated as nonsignificant risk by FDA) are minimal. Risk of potential non-response associated with lack of efficacy is managed through oversight by a trained physician. Patients will be under the care and supervision of experienced research psychiatrists and will be seen in by research clinic staff five (5) days per treatment week for treatment and assessment of worsening of symptoms/adverse events.

4) REFERENCES

1. Almeida, J. R. C. and M. L. Phillips (2013). "Distinguishing between unipolar depression and bipolar depression: current and future clinical and neuroimaging perspectives." *Biol Psychiatry* **73**(2): 111-118.
2. Altman, E. G., D. Hedeker, J. L. Peterson and J. M. Davis (1997). "The Altman Self-Rating Mania Scale." *Biol Psychiatry* **42**(10): 948-955.
3. Bernstein, D. P., J. A. Stein, M. D. Newcomb, E. Walker, D. Pogge, T. Ahluvalia, J. Stokes, L. Handelsman, M. Medrano, D. Desmond and W. Zule (2003). "Development and validation of a brief screening version of the Childhood Trauma Questionnaire." *Child Abuse Negl* **27**(2): 169-190.
4. Brignani, D., P. Manganotti, P. M. Rossini and C. Miniussi (2008). "Modulation of cortical oscillatory activity during transcranial magnetic stimulation." *Hum Brain Mapp* **29**(5): 603-612.
5. Busner, J. and S. D. Targum (2007). "The clinical global impressions scale: applying a research tool in clinical practice." *Psychiatry (Edgmont)* **4**(7): 28-37.
6. Cohen, R. B., A. R. Brunoni, P. S. Boggio and F. Fregni (2010). "Clinical predictors associated with duration of repetitive transcranial magnetic stimulation treatment for remission in bipolar depression: a naturalistic study." *J Nerv Ment Dis* **198**(9): 679-681.

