A subset of the subjects will also complete a baseline and follow-up fMRI to investigate brain functioning (pending additional funding to support the scans); participation in the brain imaging at baseline and at endpoint will be optional. fMRI procedures will consist of a one hour session in the scanner during which subjects will complete protocols for assessing resting state, emotional processing, and reward processing, which are considered core components of bipolar disorder psychopathology. fMRI procedures will occur within one week of baseline assessments and study endpoint.

The end point assessments will be completed within 5 days of the final treatment day. In final evaluation, subjects will be assessed using clinician-based interviews and self-rating scales to evaluate efficacy of the treatment. Side effects will be recorded as described by study participants at any visit or during any contact with the subjects.

Two weeks after the last sTMS treatment, subjects will be contacted by telephone for a brief follow-up safety assessment

C3. Specific Procedures or Treatments

C3a. Open Label Trial:

This study is an open label pilot study, to determine effect size for sample estimation, and determine safety and preliminary efficacy. Subjects will start treatment after baseline assessments are completed; treatment will continue for 6 treatment weeks (or until subject remits per IDSSR criterion score sustained for 14 days). A treatment week will consist of 5 treatment days within 8 calendar days. Furthermore, all subjects must have at least 5 treatments within 10 calendar days; and 30 treatments within 6 treatment weeks (plus 3 days grace period), which will lead to 45 calendar days.

Study Occasion – Open Label, not sham controlled												
Rating or procedure	Assessment Phase			Treatment Phase (week)						Termination Phase		
	Screening	MRI	Baseline	1	2	3	4	5	6	MRI	End Point	Phone Check-in
CONSENT/ELIGIBILITY	X											
SCID-5-RV	X											
Consent/MRI	X											
EEG: IAF	x											
CTQ	x											
HRSD/MADRS	X		X								X	
YRMS	X		X								X	X
BAS/BIS			X								X	
PCGI-I											X	
CGI-Bipolar			X	X	X	X	X	X	X		X	X
IDS-SR		X	x*	X	X	X	X	X	X	x*	X	
ASRM		X	x*	X	X	X	X	X	X	x*	X	
PHQ9		X	x*	X	X	X	X	X	X	x*	X	
EEG: Resting			x								X	
MRI – resting state, cerebral blood flow, reward processing, emotion processing, cognitive processing		X								X		

x* Baseline measures repeated, if needed only if >3 days from MRI or first treatment

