(1) Structured Clinical Interview for DSM-5 Research Version (SCID-5-RV) diagnoses at Screening (First et al. 2015); **(2) Hamilton Rating Scale for Depression (HRSD) 17 items**, standard depression severity rating scales by clinician interview at Baseline and End Point (Hamilton 1960); **(3) Young Mania Rating scale (YMRS)**, standard mania severity rating scales by clinician interview at Baseline and End Point (Young et al. 1978); **(4) Childhood Trauma Questionnaire (CTQ)**, self-report measure of child abuse and neglect at Baseline (Bernstein et al. 2003); **(5) Patient Clinical Global Impression for Improvement**, standard self-rating scale at End Point; **(6) Clinical Global Impressions for Severity (CGI-S)** scores by clinical rater at Baseline, Week 1-6 and End Point **and Improvement (CGI-I) Bipolar Disorder version** at End Point only (Spearing MK et al 1997); **(7) Inventory of Depressive Symptomatology (IDS-SR)**, standard self-rating scale for depressive symptoms at Baseline, Week 1-6 and End Point (Rush et al. 1996; Trivedi et al. 2004); **(8) Altman Self-Rating Mania Scale (ASRM)**, standard self-rating scale for manic symptoms at Baseline, Week 1-6 and End Point (Altman et al. 1997); **(9) Patient Health Questionnaire-9 (PHQ-9)**, standard self-rating scale for depressive symptoms at Baseline, Week 1-6 and End Point (Kroenke et al. 2001); **(10) Release of Health Information**, subject will sign releases of information for their last appointment with their PCP for medical comorbidities/ general health and for psychiatric care inpatient/outpatient for chart review for documented manic episodes; **(11) Behavioral Activation System / Behavioral Inhibition System (BAS/BIS)**, self rating scale for measures of the sensitivity of incentive and aversive motivational systems at Baseline and End Point (Carver, C. S., & White, T. L. 1994), **(12) Montgomery–Asberg Depression Rating Scale (MADRS)**, standard depression severity rating scales by clinician interview at Baseline and End Point (Montgomery and Asberg 1979)

C3c: Electroencephalogram (EEG):

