Risk of Side Effects from sTMS: Risk related to treatment with the NeoSync device is minimal. In a recently completed sham controlled trial with the same device and similar treatment schedule, both active and sham treatments were well tolerated, with no significant difference between the active and sham arms in the incidence, severity, or clinical significance of adverse events (or relationship to treatment of adverse events) reported with an incidence rate of >2%. Headache was most common, occurring in 21% of active and 19% of sham subjects, followed by back pain (8.7% active v. 4.0% sham), insomnia (6.8% active v. 5.1% sham), respiratory infection (7.8% active v. 5.1% sham), paresthesia (3.9% active v. 0% sham), nonspecific GI discomfort (3.9% active v. 3.0% sham). The Severity of these events was considered mild, and none of them resulted in a subject dropping out of the research trial. There was no significant difference in treatment discontinuation due to reported adverse events in the active versus sham groups (2 and 5 subjects, respectively). The only suicide attempt reported during the blinded trial occurred in a sham-treated subject. No SAEs were attributable to either active or sham treatment. Upon review of the available preliminary data, the FDA classified the NeoSync sTMS device as a “nonsignificant risk” device and as such there are abbreviated IDE requirements and no FDA requirement for IDE filing for the current investigator-initiated study in bipolar depression.

Risk of discomfort during EEG: Subjects may feel areas of pressure on their scalp at the location of the recording electrodes during collection of EEG data.

Risk during MRI procedures: MRI imaging is generally considered to be safe if participant does not have metallic objects in the body. Some people experience anxiety, panic or a sensation of claustrophobia when lying in the MRI machine. A separate consent form associated with use of the Brown MRI Facility will be reviewed with the subject and signed prior to participating in the scan. Subjects will also be informed that the scan provided does not constitute a clinical scan and that researchers are not board-certified neuroradiologists. The scanner also makes loud noises during imaging.

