The alternatives to participation in this study: (1) not receiving treatment for bipolar depression, or (2) receiving standard treatment administered by a clinician and/or prescribed by a physician or nurse outside of this research study. The primary risk of untreated BDD is prolonged disability and suffering, or if the condition becomes severe/worsens, possibly attempting or completing suicide. Risks related to obtaining treatment for depression outside of this study are the ones typically associated with available antidepressant and mood stabilizer pharmacotherapies, somatic therapies, or psychotherapy (side effects unique to each), and the risk of non-response to treatment interventions.

D. Protection of the Subject (include: D.1. measures to minimize potential risks; D.2 measures to ensure confidentiality; D.3. data safety monitoring plan)

D1. Measures to minimize potential risks:

Risk of Mood Destabilization: As part of inclusion criteria, subjects are required to receive stable and therapeutic doses of mood stabilizers, which should minimize TMS related mood destabilization. Furthermore, sTMS is potentially well suited to be used in bipolar disorder due to the relatively low intensity of stimulation, compared to standard rTMS. The magnetic field generated by sTMS is approximately only 10% of conventional TMS output. Moreover, in comparison, the total amount of magnetic field exposure for a full course of sTMS therapy is approximately only a minimal fraction of the exposure from a single scan with an MRI, which is widely used to study brain function in the psychiatric population, including children and infants. Furthermore, mood stability will be assessed weekly with Altman Self-Rating Mania Scale as a screening tool, and values above 6 on that screening scale will prompt further clinical evaluation that will include assessment with YRMS. Subjects will also be assessed weekly with self-rating scales for depression.

Risk of Side Effects from sTMS: A trained member of the research staff will administer each treatment and be present throughout treatment sessions to observe the participants. Moreover, all procedures will occur as part of the Butler Hospital's neuromodulation clinic, and a physician will be available at all times during treatments. Serial assessments side effects and contacts with research staff and study physicians will be used to identify and address any treatment-emergent side effects.

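### Non-mood side effects have no stated elicitation method, schedule or pre-treatment record, so their rates may be incomplete or inflated and hard to class as treatment-emergent

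*Combined protocol and SAP*

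**What the plan says.** Section A (Specific Aims) names safety first, alongside preliminary efficacy.

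**Method of recording.** C2 (Study Design) gives the only one: "Side effects will be recorded as described by study participants at any visit or during any contact with the subjects". It names no question, checklist, onset date, severity grade or judgement of relatedness.

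**Where more is relied on.**
- Human Subjects D1 (Measures to minimize potential risks): "Serial assessments side effects and contacts with research staff and study physicians will be used to identify and address any treatment-emergent side effects". It also has trained staff "be present throughout treatment sessions to observe the participants".
- Section F (Risk-Benefit Ratio): subjects are seen "five (5) days per treatment week for treatment and assessment of worsening of symptoms/adverse events".
- C2: two weeks after the last session "subjects will be contacted by telephone for a brief follow-up safety assessment". In the flow chart that call carries only the mania rating and CGI-Bipolar.

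**What is scheduled.** The flow chart in C3a has no side-effect or adverse-event row at any visit. None of the twelve numbered items in C3b is a side-effect instrument. C4 (Data Analysis) has no adverse-event summary.

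**Mood symptoms are treated differently.** D1 says "mood stability will be assessed weekly with Altman Self-Rating Mania Scale as a screening tool", and C3b lists that scale as a "standard self-rating scale for manic symptoms at Baseline, Week 1-6 and End Point". The YMRS is taken before treatment and at End Point, and the flow chart adds it at the phone check-in. The IDS-SR and PHQ-9 are taken before treatment, weekly and at End Point.

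**Reference rates.** Potential Risks (Human Subjects, section C) describes tolerability in a sham-controlled trial of the same device by physical and sleep complaints, for example "insomnia (6.8% active v. 5.1% sham".

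**The concern.** D1 and section F depend on a procedure that no section describes. C2, which should describe it, refers only to what participants describe. Two consequences follow for events outside the mood scales.

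First, if staff do not ask a standard question, mild complaints that arise between sessions are counted only when a subject mentions them. Second, with no specified record of complaints before treatment, there is no stated comparison by which an event is new. Insomnia shows the difficulty. Section B (Background) lists disturbed sleep among the features of the depressed phase, and Potential Risks lists insomnia as an event seen on the device.

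There is no control arm to reveal an error in either direction. A clean or a poor tolerability profile could therefore partly reflect how events were collected. A baseline record cannot be recovered once treatment has begun.

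**Working it through.** The plan states no safety rate, power or precision, and C4 says that the sample size does not come from a significance calculation. There is no figure to reproduce. The passages are compared first; the arithmetic then only shows scale.

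**1. Passages side by side**

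| Element needed | Manic and depressive symptoms | Other side effects |
|---|---|---|
| Instrument or standard question | ASRM, YMRS, IDS-SR, PHQ-9 | None named |
| Pre-treatment record | Yes | None specified |
| Scheduled repeats | Weekly (ASRM, IDS-SR, PHQ-9) and End Point | Contact five days per treatment week; content not specified |
| Definition of emergent | Change from a scored baseline is available | None |
| Analysis in C4 | Depression scales only | None |

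**2. Effect of incomplete capture**

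Inputs: n = 20 (C4) and active-arm rates p (Potential Risks). The capture share s is an assumption. Expected subjects = 20 × p × s. Chance of seeing at least one = 1 − (1 − p × s)^20.

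| Event | p | Expected, s = 1 | Expected, s = 0.5 | At least one, s = 1 | At least one, s = 0.5 |
|---|---|---|---|---|---|
| Headache | 0.21 | 4.20 | 2.10 | 99% | 89% |
| Back pain | 0.087 | 1.74 | 0.87 | 84% | 59% |
| Respiratory infection | 0.078 | 1.56 | 0.78 | 80% | 55% |
| Insomnia | 0.068 | 1.36 | 0.68 | 76% | 50% |
| Paresthesia; GI discomfort (each) | 0.039 | 0.78 | 0.39 | 55% | 33% |

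At s = 0.25, expected headaches fall to 1.05 and the chance of seeing any back pain to 36%.

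**3. Effect of no baseline record**

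Let b be the assumed share with headache before treatment. Up to 20 × b subjects could be wrongly counted as emergent: 1 at b = 0.05, 2 at b = 0.10, 6 at b = 0.30.

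**4. Both together**

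Apply p = 0.21 to subjects free of headache at the start, and the same s to old and new complaints. True emergent share = (1 − b) × 0.21. Recorded share = s × [b + (1 − b) × 0.21].

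- b = 0.10, s = 0.5: true 0.90 × 0.21 = 18.9%; recorded 0.5 × 0.289 = 14.5%. Too low.
- b = 0.30, s = 0.75: true 0.70 × 0.21 = 14.7%; recorded 0.75 × 0.447 = 33.5%. Too high.

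The sign of the error depends on two quantities that the documents do not give.

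**5. Precision in any case**

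Exact 95% intervals at n = 20: 4/20 gives 5.7% to 43.7%, and 2/20 gives 1.2% to 31.7%. The quoted active and sham headache rates differ by 20 × (0.21 − 0.19) = 0.4 expected subjects.

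**The case against.** The best defence is that the sections can be read together: staff see subjects almost daily, assess adverse events, and record the answers in the subject's words. C2 does not say that staff will not ask. The flow chart also omits the treatment sessions themselves, so a missing row does not prove a missing activity. Recording at any visit does not exclude Screening or Baseline, and C3b obtains primary-care records on general health.

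Much of this stands, and it rules out several stronger readings that a reader might infer:

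- **That collection is purely passive.** D1, section F and the phone call all describe assessment. What is missing is its content. Frequency of contact is not a method, and watching a 30-minute session cannot detect insomnia or a headache that comes later.
- **That the safety aim will rest on under-counts.** Under-counting is possible but not established, and a missing baseline pushes the other way.
- **That events cannot be called treatment-emergent.** Onset dates taken at near-daily visits could support the label. The plan does not say that they will be taken.
- **That the mood-switch question is compromised.** Mood destabilization, the risk stressed for this population, has pre-treatment and repeated scale measures.

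The depression scales might also help with sleep complaints, but the documents do not list their items and C4 analyses the depression scales by total score and by IDS-SR response and remission.

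Two further points stand. The plan proposes no comparison with the earlier trial's rates and does not say how that trial elicited events, so a checklist here might weaken comparability rather than restore it. And attribution from 20 subjects in one arm is weak under any form of collection.

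**Conclusion.** The point holds for non-mood events: headache, back pain, insomnia, paresthesia, GI discomfort, respiratory infection and the like. For these the plan does not specify how they are elicited, when, or against what baseline, although D1 and section F rely on that being done and safety is the first-named objective. Their rates may be incomplete or inflated, and the net direction is unknown.

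The size cannot be fixed from the documents. For the commonest event, halving capture would remove about 2 of 4.2 expected cases, and an assumed 10% prior prevalence could add up to 2. Either shift is large against counts this small. The capture share, the prior prevalence and the carry-over of the earlier trial's rates to this population are all assumptions. Manic and depressive symptoms are adequately baselined and are not part of the problem.

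This should be corrected, but it does not undermine the design. It is more than missing detail, because a better method is available at little cost and the baseline record has to be taken before the first session.

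**What to change.** 1. **C2.** Replace the sentence on side effects with standard elicitation: one open question, then a short checklist of every event listed in Potential Risks (headache, back pain, insomnia, respiratory infection, paresthesia, GI discomfort). Record onset date, severity and relation to treatment. Keep spontaneous reports in addition.
2. **C3a flow chart and C3b.** Add the item at Baseline, the end of each treatment week, End Point and the phone check-in. Have D1 and section F refer to it, so that all sections describe one procedure.
3. **Definition.** State that treatment-emergent means new, or worse than the Baseline record.
4. **C4.** Report the number and percentage of subjects with each treatment-emergent event, with exact 95% intervals.

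**Cost.** One flow-chart row, a one-page form and a few minutes per week from staff who already see each subject on every treatment day. Sample size and treatment schedule do not change. Reported event rates will probably be somewhat higher. Any comparison with the earlier trial's rates needs caution, because the documents do not say how its events were elicited.

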A total of 20 subjects will be enrolled and treated. The sample size for this open-label study is based on estimations regarding the appropriate amount of information required to inform next steps in trial design rather than on statistical significance calculations for any primary safety or efficacy endpoint. For the primary efficacy endpoint, we will analyze change in total scores on the IDS-SR, HRSD, and MADRS scores from baseline to End Point. Categorical response (50% decrease from pre-treatment baseline on IDS-SR) and Remission (IDS-SR score <14) will be calculated to determine treatment efficacy.

Neuroimaging data will be pre-processed and analyzed using statistical parametric mapping software SPM5 (<http://www.fil.ion.ucl.ac.uk/spm>). For both experiments, a first-level effect model will be constructed with conditions entered separately in the design matrix.

D. Material Inducements

Subjects will not be compensated for the sTMS treatment but rather receive it free of charge. Subjects that participate in each neuroimaging session will receive a gift card with value of \$25 for each MRI scan they complete.

E. Training of Research Personnel

Clinical data will be collected, entered and analyzed by [name] in the Mood Disorders Research Program and research assistants trained under his supervision. Neuroimaging data will be processed and analyzed by [name] and research assistants trained under his supervision. [name] will provide overall supervision and oversight for the study.

3) Human Subjects**A. Subject Population** *(include number; gender; age; diagnosis; inpatient vs. outpatient; physical health; inclusion/exclusion criteria; rationale for use of special groups)*

A total of 20 male and female subjects, age 18 to 80 years, who are suffering from bipolar disorder type 1, currently depressed, will be enrolled into the study and treated. All subjects will receive open label sTMS treatment. Subjects will be recruited from outpatient setting and in stable physical health.

Inclusion Criteria: Subjects must meet all of the following inclusion criteria to qualify for enrollment into the study:

- (1) 18 – 80 years of age;
- (2) DSM-5 primary diagnosis of Bipolar Disorder type 1 (with a documented diagnosis of the disorder on medical record), currently in a Major Depressive Episode by diagnostic criteria elicited by structured clinical interview (SCID-5-RV);
- (3) MADRS score ≥ 20 ;
- (4) Duration of current episode ≥ 4 weeks
- (5) YMRS score ≤ 12 ;

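### Does the disagreement over mania ratings at the two-week phone check-in, with no safety summary in C4, call for a change to the plan?

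*Combined protocol and SAP*

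**What the plan says.** C2 describes the last contact as follows: "Two weeks after the last sTMS treatment, subjects will be contacted by telephone for a brief follow-up safety assessment". It does not say which scales are used. The schedule table in C3a does. It marks the YMRS (spelled YRMS there) at Screening, Baseline, End Point and Phone Check-in, and CGI-Bipolar at Baseline, weeks 1 to 6, End Point and Phone Check-in. The ASRM has no phone entry.

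C3b gives the YMRS as "standard mania severity rating scales by clinician interview at Baseline and End Point" and the CGI-S as "scores by clinical rater at Baseline, Week 1-6 and End Point", and confines the CGI-I to End Point. It ties no instrument to the phone call.

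On timing, C2 says "The end point assessments will be completed within 5 days of the final treatment day", and C3a limits a full course with the words "which will lead to 45 calendar days". C2 also has side effects recorded whenever study staff are in contact with a subject. D1 uses the weekly ASRM as a screen, with a score above 6 leading to clinical evaluation and a YMRS.

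On purpose, C3a says "This study is an open label pilot study, to determine effect size for sample estimation, and determine safety and preliminary efficacy". C4 explains that the sample size rests on the information needed for the next trial "rather than on statistical significance calculations for any primary safety or efficacy endpoint". For efficacy it says "we will analyze change in total scores on the IDS-SR, HRSD, and MADRS scores from baseline to End Point", then adds IDS-SR response and remission and the imaging processing. It describes no summary of mania scores, adverse events or withdrawals.

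**The concern.** Mood destabilization is the first risk that the protocol lists, and the background notes reports of mania after conventional TMS and says that sTMS has not been studied in bipolar disorder. The phone call is the only scheduled contact after End Point and the only one described as a safety assessment. Read literally, C3b leaves it without a mania scale, because the ASRM is not scheduled there in either place.

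A table can be added at analysis, but a rating that was never taken cannot be recovered. If some subjects were followed by the table and others by C3b, a count of manic or hypomanic switches would cover unequal windows. C4 does not settle the matter, because it does not say which safety ratings or which window are to be reported.

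**Working it through.** **Calendar.** Inputs: first session on day 1 (C2), full course of at most 45 days (C3a), End Point up to 5 days after the last session (C2), phone call 14 days after the last session (C2).

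- The plan's own figure: 6 weeks × 7 days + 3 grace days = 45. It is reproduced.
- Latest End Point: 45 + 5 = day 50. Phone call: 45 + 14 = day 59.
- Gap between End Point and call: 59 − 50 = 9 days to 59 − 45 = 14 days, that is 9/59 = 15.3% to 14/59 = 23.7% of follow-up.
- C3a also defines a treatment week as 5 sessions within 8 calendar days. Taken literally, 6 × 8 + 3 = 51, which gives day 56 and day 65. The gap stays at 9 to 14 days.
- Early remitter, assuming the last session is on day 21: phone call on day 21 + 14 = 35, and a gap of 9/35 = 25.7% to 14/35 = 40.0% of a shorter follow-up.

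**What depends on the reading.** Scheduled post-baseline assessments for a full course, leaving aside conditional repeats around the MRI:

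| Scale | Weeks 1–6 | End Point | Phone, table | Phone, C3b |
|---|---|---|---|---|
| ASRM | 6 | 1 | 0 | 0 |
| CGI-Bipolar | 6 | 1 | 1 | 0 |
| YMRS | 0 | 1 | 1 | 0 |
| Total | 12 | 3 | 2 | 0 |

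The table gives 12 + 3 + 2 = 17 and C3b gives 12 + 3 = 15. The reading decides 2 of 17.

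**Is C3b a complete schedule?** It omits the Screening YMRS, HRSD and MADRS, all marked in the table, although eligibility requires a MADRS of at least 20 and a YMRS of at most 12. It places the CTQ at Baseline where the table has Screening. It also omits the IDS-SR, ASRM and PHQ-9 marked in the table's first MRI column. A list with these omissions is weak evidence that the phone ratings were deliberately excluded. The restriction of the CGI-I to End Point does not contradict the table, whose CGI-Bipolar row does not separate severity from improvement; a severity rating by phone satisfies both.

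**Does the missing rating change a denominator?** A subject with any weekly ASRM or an End Point YMRS has a post-baseline mania rating without the phone call. If all 20 have at least one, a descriptive proportion has N = 20 on either reading. With no events, the exact two-sided 95% upper limit is 1 − 0.025^(1/20) = 16.8% both ways. Only the length of the window differs, and that already varies by design: 35 days for the early remitter above against 59 for a full course.

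**The case for a change.** The best case for acting is that C3b agrees with the table on weeks 1 to 6 and End Point for the other scales, apart from the conditional repeats around the MRI. The phone ratings are therefore the one real post-baseline difference, and they fall at the contact described as a safety assessment. No sentence says which list governs, a lost rating stays lost, and the cost of aligning two rows with two sentences is small. Separately, a plan with safety in its objective should say how safety will be summarized.

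Much of this stands as description. The lists differ, and C4 is silent on safety. What does not follow is a wrong result. The plan contains no switch proportion for unequal windows to distort, and the silence in C4 does not cause the day 50 or day 59 difference. Asking only that the lists be reconciled would not say which to keep, and the table as written already provides the phone rating. Adverse events, withdrawals, ASRM scores above 6, and YMRS and CGI-Bipolar by visit can all be tabulated from data the protocol collects, with each subject's last rating date shown.

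**Conclusion.** No change to the plan follows. The mismatch is best read as a clerical slip in a shortened instrument list, and the missing safety summary as a gap that analysts of a small descriptive pilot fill sensibly. At most, two assessments per subject are in doubt, at one contact 9 to 14 days after End Point. Spontaneous reports of side effects are still captured at that contact, and the 15 earlier scheduled assessments are untouched. Efficacy results are unaffected.

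This rests on three assumptions: staff work from the schedule table, subjects have at least one post-baseline mania rating, and the report states the follow-up window actually used. If the phone ratings were skipped for some subjects, the safety description would stop at End Point for them. That would be a limitation to report. With no control arm, any switch count is descriptive and cannot be attributed to sTMS under either schedule.
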